Preventing Attrition and Reducing Burden. We will use strategies for enhancing retention ¹⁸⁴ such as meeting with participants to discuss the study and answer any questions (e.g., implications of randomization, roles of C-CBSM & CBSM, nature of intervention, psychosocial & biological assessments, homework assignments, study benefits & risk, etc.). To prevent participant drop-out and reduce burden, we will use recommendations for enhancing clinical trial retention ¹⁸⁴ such as meeting with the participants in individual sessions at our recruitment sites during scheduled visits or speaking with them via telephone as requested to discuss study participation and answer any questions (e.g., implications of random assignment, roles of C-CBSM & CBSM, duration & nature of intervention, rationale for the psychosocial & biological assessments, homework assignments, study benefits & risk, etc.). We have found that regular contact with participants improves retention rates. We also have multiple strategies to prevent attrition and reduce participant burden. Understanding that this is an older, co-morbid population facing multiple contextual barriers, we have taken steps to address the multiple challenges and barriers that may lead to participant burden, prevent participation or promote attrition. These strategies include providing transportation for assessment or intervention visits for up to 30% of the sample. This will provide us with the flexibility to offer participants the option of receiving transportation services to attend our clinic or intervention visits. In our past work we have found that about 30% of all PC survivors make such requests; however, we will actively promote such accommodations to ease participation burden and reduce attrition. In addition to these accommodations, we follow procedures as we have in all our prior cancer survivorship studies where we provide snacks, refreshments and breaks during our assessments and intervention sessions, and provide flexible appointment schedules (e.g., weekends) to maximize participation, reduce burden and prevent attrition. We will also offer participants the option of completing a shorter version of the study assessment in person or by telephone. Telephone assessments will be determined on a case by case basis by the PI or Co -PIs who will assess the level of difficulty the participant has in completing the entire assessment face to face, for example unforeseen changes in employment and/ work schedule, health issues, relocation, unforeseen transportation difficulties, family crisis, social/environmental/health crisis (COVID-19), etc. Group facilitators will also reach out to participants via "booster" telephone calls in between participants' T-2 through T-3 in person interview and T-3 through T-4 in person interview. The "booster" calls will serve as a mini-review session with participants to discuss content covered in the group sessions. Phone scripts for the booster calls are in the development by study staff and will be sent to PMRC and UM IRB in the next modification for approval. Study staff will also conduct two check-in calls to discuss general comments and/or concerns a participant may have; these check-in calls will also serve to remind participants of their next in-person assessment. The first check-in call will take place four weeks after the completion of the 10-week group sessions, while the second check-in call will take place four weeks after the second phone booster call. We will make every effort for participants to complete their follow-up assessments within their expected timeline (see Assessment and Data Collection section), however we anticipate that some participants will require additional 2 months to accommodate for life changes. If a participant's follow-up assessment passes the extra 2 months period we will attempt to collect the next timepoint assessment. We will also encourage participants to complete all follow-up assessments however we anticipate that some participants may encounter difficulties in completing an assessment at the scheduled timepoint due to multiple circumstances, such as unforeseen changes in employment and/ work schedule, health issues, relocation, unforeseen transportation difficulties, family crisis, social/environmental/health crisis (COVID-19). We will make sure that these participants are still willing to continue participating in the study and review their assessment timeline regularly. We will continue to assess the participant's interest in continuing in our study via check-in calls and booster calls. Collectively, these strategies are designed to address the multiple medical and contextual challenges that our targeted sample is likely to be facing and thus promote study participation with minimal burden to the participant.

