
Additional Retention Strategies: Participants who may be experiencing multiple challenges (e.g., financial, access to care, comorbid illness, etc.) present special problems for which alternative procedures are required in order to maximize retention. As mentioned above we will be compensating participants for their assessment visits, and mailing them follow-up reminder cards two to three weeks before their subsequent appointments. If a participant does not call to make an appointment for re- assessment, the contact staff will call on the individual indicated as primary contact by the participant. This contact may take place through telephone or face-to-face. The staff person making the call will attempt to collect information that will lead to location of the participant. Secondary and tertiary contacts named in the participant's locator files will also be part of the contact staff's repertoire for finding a seemingly lost participant. In the event that cancer or other medical condition hinders a participant's ability to attend an assessment visit, we will offer them the option of home visits for data collection. In all such cases, we will respect the participants' right to refuse this option and will be acutely sensitive to their desire to maintain their privacy during these difficult times. If the participant does consent to home visits, we will furnish the personnel to visit them. If the full battery of tests is too burdensome, we will use an abbreviated battery consisting of our primary outcome measures. For participants who refuse to return for assessments or who have dropped out of the study, we will offer them the opportunity to schedule their assessment at any time of day at the most convenient location and will offer them the opportunity to complete only the abbreviated form of the battery should they so request. We will also respect a participant's refusal to undergo blood draws. Repeated failure to locate a participant for follow-up will lead to our contacting the Florida Departments of Health to learn of death certificates issued in the period since the missed assessment.

Data Analysis Plan including Statistical Procedures Study Hypotheses:

Hypothesis 1 (Aim 1): C-CBSM will show significantly greater reduced symptom burden and improved HRQoL from baseline (T1) to 3-, 6- and 12-month follow-ups (T2-T4) relative to CBSM.

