Hypothesis 2 (Aim 2): C-CBSM will show significantly greater improvements in intervention targets (i.e., improved stress management, and reduced psychological distress and interpersonal disruption) from baseline (T1) to 3-, 6- and 12-month follow-ups (T2-T4) relative to CBSM.

Test of Study Hypotheses. All analyses will be intent-to-treat analyses ¹⁹⁸ and linear mixed models will be used to test Hypotheses 1-2. These models classify time of measurement as a categorical variable in order to give full flexibility to different mean time courses in the two randomized groups. Latent growth modeling (LGM)¹⁸⁵ with relevant covariates is used to test the three sub-hypotheses of Aim 4. Advances in LGM and structural equations modeling (SEM)¹⁸⁶ allow us to blend these methods to test complex models of change¹⁸⁷ as latent growth models. LGM allows for missing data, as well as irregularly spaced measurements across time, time-varying and invariant covariates, accommodation of individual-specific deviations from the mean time trend and estimation of population variance associated with individual effects. Analyses of the first 3 hypotheses inform the functional form of the LGM time course. Software to implement these analyses is available (e.g. Mplus). ^{188,189} The software permits the blending of continuous and categorical data, the specification of linear and nonlinear models of change, and the specification of longitudinal structural models. Adequate model fit will be established by several fit indicators (Comparative Fit Index [CFI] > .95, Root-Mean-Square Error of Approximation [RMSEA] ≤ .05, Standardized Root-Mean-Square Residual [SRMR] < .08). ¹⁹⁰

Exploratory Hypotheses:

Hypothesis 3 (Aim 3): C-CBSM will show significantly greater activation of leukocyte glucocorticoid receptor (i.e., greater sensitivity) and lower inflammatory gene expression (i.e., less activation) pathways from baseline (T1) to 3-, 6- and 12-month follow-ups (T2-T4) relative to CBSM.

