0.81 and 0.42 respectively. With greater effect sizes anticipated in the proposed study, the sample size of at least 100 per arm has sufficient power to detect differences even after adjusting for the analysis of change from baseline to post-intervention time points. Power for C-CBSM's effect on down regulation of inflammatory genes are based on Antoni et al.¹²⁴ study which indicated that the observed effect size was one standard deviation in a sample size of 45 in the experimental condition. Glucocorticoid receptor sensitivity demonstrated similar effects. With a T4 sample size of 100 in the C-CBSM group, effect sizes of 0.48 standard deviations are detectable with 80% power at a 2-tailed Type I error rate of 1%, so that expected effects will be detectable with sufficient power. While pilot data are not available for all outcome measures, the constant in the power calculation regardless of the outcome is the effect size expressed in terms of standard deviations, which is 0.40 or 0.49 depending on whether the Type I error rate is 5% or 1%.

Covariates, Cohort Effects, Intent to Treat & Missing Data. A number of variables (e.g., SES, disease factors) will be considered as possible covariates. These putative confounds will be entered as covariates if correlated with our outcomes (at p<.10). Random assignment should render groups equivalent on covariates and this will be verified post-hoc. We will test differences among cohorts who have completed our conditions by doing an ANOVA within each condition with k levels of cohort. If we find a cohort with differential outcomes (significant Condition x Cohort x Time interaction), we will conduct a Group x Time interaction tested within each cohort, and a Cohort x Time interaction tested within assignment. We have never observed a significant cohort effect in prior CBSM work. We will also use an intent-to-treat approach in that all participants will be retained in the analysis, including those with missing data at time points by using full information maximum likelihood (FIML) estimation. FIML, a recommended state-of-the-art method, 197,198 uses all available data for each participant and provides unbiased estimates of parameters when the data are missing at random.

Cost to the Participants:

There will be no cost to the participants for taking part in this study. All expenses related to the study activities, including laboratory tests done and lab materials.

Risk and Benefits:

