Given the time demands of this study, we will offer compensation of \$75 at each assessment visit, for a total of \$300 for study participation. Participants who are able to complete the entire interview (blood work and questionnaire) will receive \$75. Participants who complete 75% of the interview (blood work and the socio-demographic, health related, stress/distress questionnaires) will receive \$50. Participants who complete the other 25% of the interview (Interpersonal, Mechanics, Culture, and Other sections) will receive \$25 upon completion. We will also provide parking or transportation for assessment or intervention visits for up to 30% of the sample. This will provide us with the flexibility to offer participants the option of receiving transportation services to attend our clinic or intervention visits. Participants will not be paid for those research activities that they do not complete. However, they will not incur any additional costs for being in our study.

Vulnerable Populations:

N/A

Withdrawal of Subjects:

Participation in study is completely voluntary where participants can elect not to answer any specific question on the questionnaire. It is also voluntary to complete the questionnaire/test/specimen banking and can elect to not participate at all in the study.

Data & Safety Monitoring:

The informed consent, all assessment measures, and intervention modules have been reviewed and approved by the UM Institutional Review Boards (IRB). In addition, the study will be closely monitored by the Sylvester Comprehensive Cancer Center (SCCC) Data and Safety Monitoring Committee (DSMC) in accordance to the Cancer Center's Data and Safety Monitoring Plan (DSMP) and a Community Advisory Board (CAB). In its oversight capacity, the DSMC bears responsibility for suspending or terminating this study. DSMC oversight of the

conduct of this trial includes ongoing review of adverse event data, and periodic review of the study's aims (refer to Data Analysis section). The guidelines appearing in this section are offered for DSMC consideration in assessing adverse events and treatment response or other study endpoint. In addition, the DSMC will review reports from all audits, site visits, or study reviews pertaining to this clinical trial and take appropriate action. The SCCC DSMC to which this study is subject can be found at www.sccc.org.

Community Advisory Board (CAB):

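### The abbreviated battery leaves every Aim 2 target unscored and the Hypothesis 2 model makes no use of the primary scores saved at those visits, so the Aim 2 contrast can be biased if switching follows health

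*Combined protocol and SAP*

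**What the plan says.** **The short form.** Additional Retention Strategies first offers a home visit: "In the event that cancer or other medical condition hinders a participant's ability to attend an assessment visit". It then adds: "If the full battery of tests is too burdensome, we will use an abbreviated battery consisting of our primary outcome measures". For men who refuse or have dropped out, staff "will offer them the opportunity to complete only the abbreviated form of the battery should they so request".

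**What is in it.** The primary outcomes section lists EPIC-S, EPIC-UIN, FACT-P and the PROMIS pain and fatigue short forms. The intervention-targets section lists MOCS, MAX-PC, PROMIS Depression and Anxiety, and SIP. The two lists share no measure.

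**Other shortened assessments.** Preventing Attrition and Reducing Burden says: "We will also offer participants the option of completing a shorter version of the study assessment in person or by telephone". It does not give the content. Participant Compensation has a partial tier: "Participants who complete 75% of the interview (blood work and the socio-demographic, health related, stress/distress questionnaires". The remainder is described separately: "Participants who complete the other 25% of the interview (Interpersonal, Mechanics, Culture, and Other sections) will receive".

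**The hypothesis and model.** Hypothesis 2 states that "C-CBSM will show significantly greater improvements in intervention targets" from T1 to T2-T4. It is tested with a linear mixed model per outcome (Test of Study Hypotheses). Under To Test Exploratory Hypotheses, Hypotheses 1 to 3 share one form: group, time, their interaction and a person effect with compound symmetry. Possible covariates are illustrated by SES and disease factors. For missing data the plan relies on FIML, which "uses all available data for each participant and provides unbiased estimates of parameters when the data are missing at random". It names no auxiliary variables and no sensitivity analysis.

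**The concern.** When the abbreviated battery is used, the primary outcomes are observed and every Aim 2 target is missing by design. The stated triggers are burden, medical condition and refusal, so a man's current health plausibly influences which battery he takes. Health is also expected to correlate with the targets: Hypothesis 4a assumes that link.

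Missing-at-random is a property of a model together with the data it conditions on. A model holding only MOCS scores cannot use the FACT or fatigue score that may explain why MOCS is absent. If health drives the switch, the condition fails for that model even though the explaining variable is in the database.

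Aim 2 is the only aim listed under the Secondary heading, so its contrast is worth protecting.

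**Working it through.** **1. The plan's own figure.** Power Analyses gives 100 per arm, two-sided, effects in SDs of change. Power = Φ(d·√(n/2) − z).
- d = 0.40, 5%: 0.40 × 7.071 − 1.960 = 0.868, power 80.7%.
- d = 0.49, 1%: 0.49 × 7.071 − 2.576 = 0.889, power 81.3%.

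Both stated figures reproduce. The standard error of the contrast is √(2/100) = 0.141.

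**2. Precision cost.** If 10% or 20% of men give no target score (assumed; complete-case approximation), n per arm is 90 or 80 and power at 0.40 and 5% is 76.5% or 71.6%.

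**3. How bias arises.** Assumptions: four visits; correlation 0.6 between visits within a measure; same-visit target-health correlation r; target missing at T2-T4 when health at that visit is below a cut-off c. The SD of change is √(2 × (1 − 0.6)) = 0.894. The mean of the observed targets is shifted up by r·φ(c)/(1 − Φ(c)).
- CBSM, 20% switching: c = −0.842, shift 0.280/0.800 × r = 0.350r.
- C-CBSM, health better by 0.40 SD of change (0.358 raw): effective c = −1.200, 11.5% switching, shift 0.194/0.885 × r = 0.219r.
- Difference: −0.131r raw, or −0.146r in SDs of change. At r = 0.5 this turns 0.40 into about 0.33.

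That is a complete-case figure. A likelihood model recovers part of the loss from the target's own history, so simulation is needed.

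**4. Simulation, common cut-off and health benefit of 0.40.** 50,000 per arm, simulation error about 0.01, true target effect 0.40. Planned compound-symmetry model:

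| Switching in CBSM (C-CBSM) | r = 0.3 | r = 0.5 | r = 0.7 |
|---|---|---|---|
| 10% (5%) | 0.389 | 0.370 | 0.355 |
| 20% (12%) | 0.368 | 0.353 | 0.330 |
| 30% (19%) | 0.371 | 0.337 | 0.320 |

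Adding the health score to the likelihood gives 0.395 to 0.407 in all nine cells.

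A softer version (100 per arm, logistic switching at T4 only, 15% or 30%) gives 0.356 to 0.394 for the target-only analysis and 0.395 to 0.403 with FACT added, at about the same standard error.

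**5. Other patterns** (r = 0.3 / 0.5 / 0.7):

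| Pattern | Planned model | Health score added |
|---|---|---|
| Alike in both arms (20%), no arm effect on health | 0.410 / 0.396 / 0.406 | 0.406 / 0.399 / 0.403 |
| 20% in C-CBSM, 10% in CBSM | 0.434 / 0.456 / 0.489 | 0.399 / 0.398 / 0.405 |
| 10% in C-CBSM, 20% in CBSM | 0.356 / 0.339 / 0.314 | 0.388 / 0.397 / 0.397 |
| True effect 0; 20% in C-CBSM, 10% in CBSM | 0.011 / 0.067 / 0.084 | −0.020 / 0.011 / 0.001 |
| Step 4 pattern at 20%, driver outside the auxiliary set | 0.369 / 0.354 / 0.341 | 0.381 / 0.375 / 0.368 |
| 20% in C-CBSM, 10% in CBSM, driver outside the auxiliary set | 0.429 / 0.444 / 0.484 | 0.415 / 0.421 / 0.451 |

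**6. Size against noise.** The step 4 shift of 0.011 to 0.080 is 0.08 to 0.57 of the 0.141 standard error.

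**The case against.** The short form is a deliberate and sensible trade. It is conditional or on request, a home visit comes first for ill men, and the alternative may be no data. The documents do not say that primary scores drive the switch. The retention sections also cite finances, access to care, employment, relocation, transport and family crisis. A simulation that lets one health score drive switching and then hands that score to the model will recover the truth; the last two rows of step 5 show that otherwise the bias is only partly removed. The missing-data section states missing-at-random as a condition, not a fact. All of this stands. It makes the bias a risk rather than a certainty, but it does not explain why scores already collected should go unused.

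Four stronger readings are tempting, and the documents do not support them.
- **That Hypothesis 4a fails in the same way.** Its growth model holds the mediator and the tested primary outcome together, so FIML already uses that outcome. Only primary scores outside the particular model are unused, such as fatigue when EPIC-S is the outcome.
- **That the 75% interview tier loses all Aim 2 targets.** It keeps the stress/distress questionnaires. What it clearly loses is the Interpersonal section and the others listed with it. Where MOCS sits is not stated.
- **That 22% to 30% of men take the short form.** Those figures (attrition of about 22%; 140 of 200 retained, so 60/200 = 30% lost) describe loss to follow-up. Men lost entirely have no primary scores at that visit either.
- **That Aim 2 is biased towards zero by as much as 43%.** An estimate near 0.23 needs health-driven switching in one arm only and targets absent at every follow-up. Nothing in the documents points to that pattern, and step 5 shows that bias can also be upward or absent.

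**Conclusion.** The concern holds for Hypothesis 2. The abbreviated battery omits all its endpoints, and the planned model does not use the primary scores recorded in their place. Whether this biases the contrast depends on two things the documents do not give: how often the short form is used, and whether its use follows health.

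With 10% to 30% use assumed, target-health correlation of 0.3 to 0.7, a common health-driven mechanism and an arm effect on health, a true 0.40 SD is estimated at about 0.33 to 0.39, and 0.32 at 30% use with correlation 0.7. Hypothesis 1 predicts such an arm effect, so this pattern is plausible under the study's own expectations. With switching alike in both arms and no arm effect on health, there is no bias. With rates of 20% against 10%, estimates run from 0.31 to 0.49 depending on which arm switches more. The effect on Hypothesis 4a is confined to primary scores outside the particular growth model.

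This is a modest risk to the secondary aim that can be reduced cheaply, not a flaw that invalidates it.

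**What to change.** 1. For Hypothesis 2, name a small set of same-visit primary scores, for example FACT total and PROMIS fatigue, as auxiliary variables in the FIML model. Alternatively, use them in multiple imputation by arm, followed by the planned mixed model. Do not enter them as adjusted covariates: they are measured after randomization and may carry part of the intervention effect.
2. Keep the set small. All five primary scores at four visits give 20 auxiliaries; with four target values that is 24 variables and 24 + 24 × 25/2 = 324 means and covariances, too many to fit by arm with 100 men. Two scores give 12 variables and 12 + 12 × 13/2 = 90.
3. Record and report battery version and reason by arm and visit. State whether the abbreviated battery, the shorter assessment and the 75% tier are the same thing, and which targets each contains.
4. Optionally, add MOCS to the abbreviated battery, so that one Aim 2 endpoint is scored for everyone assessed. This adds a little burden for men who asked for less; the analysis change stands without it.

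The cost is some analysis wording, a slightly larger model and one logged field. The correction is only partial if switching is driven by factors outside the auxiliary set, and it cannot help where no primary score was obtained.
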